2.4 Determination of Sample Size

No sample size calculation was done. Sample size was dependent upon recruitment into and completion of preceding studies. At the time of development of this SAP, the study enrollment has been completed; a total of 668 subjects were enrolled into N01199.

3 DATA ANALYSIS CONSIDERATIONS

3.1 General presentation of summaries and analyses

Statistical analysis and generation of tables, figures, subject data listings, and statistical output will be carried out using SAS® Version 9.1 or higher.

Descriptive statistics, such as the mean, standard deviation (SD), median, 25th percentile, 75th percentile, minimum value, and maximum value for quantitative variables, and counts and percentages for categorical variables, will be provided. Denominators for percentages will generally be based on the set of subjects with at least 1 assessment at the time point or at least 1 assessment during the time interval being summarized.

All summaries will be descriptive; no statistical hypothesis testing is planned.

Unless otherwise noted, summaries will present BRV overall, which will include all subjects exposed to BRV during the study.

Subject data listings will be provided and will present source data and key derived variables for statistical analyses.

3.2 Analysis time points

3.2.1 First and last dose of BRV

Unless otherwise noted, all references to the first dose of BRV in this SAP refer to the first dose of BRV during N01199 (ie, not the first dose of BRV from the previous study in which subjects participated in prior to N01199). Unless otherwise noted, all references to the last known dose of BRV in this SAP refer to the last dose of BRV taken across any study periods (ie, not necessarily the last dose of BRV during the Evaluation Period).

3.2.2 Relative day

Relative day will be calculated as the current date minus the date of first dose of study drug for days prior to the first dose of study drug, and the current date minus the date of first dose of study drug plus 1 for days on or after the day first dose of study drug and prior to or on the day of last study drug dose (eg, the day of first dose will be Day 1 and the day prior to first dose will be Day -1), ie, Day 1 representing the day of first dose of BRV, the previous day is Day -1 and each day prior to that is Day -2, Day -3, etc; subsequent relative days to Day 1 will be Day 2, Day 3, etc. For days after the last dose of BRV, relative day will be calculated as the current date minus the date of last dose of BRV and including a '+' to denote post treatment days (eg, the day after the last dose of BRV will be Day +1). Relative day will not be calculated for partial or missing dates.

3.2.3 Study Entry Visit

The study Entry Visit (EV) corresponds to assessments performed at the time of entry into N01199. There are 3 groups of subjects to consider:

1. Subjects who immediately entered N01199 after completing the Treatment Periods for N01193, N01252, N01253, and N01254.
2. Subjects who entered the Down-Titration Period of the previous study and entered N01199 during the Down-Titration Period.
3. Subjects who did not immediately enter N01199 and had a gap in treatment with study drug between the previous study and N01199.

Subjects in Categories 1 and 2

Subjects in categories 1 and 2 will generally not have any interruption in study drug dosing during the transition to N01199. For such subjects, selected assessments from the following visits from the previous study will be summarized at EV:

| Study | Visit (Time Point) |
|---------------|---------------------------|
| N01193 | Visit 4 (Week 7) |
| N01252/N01253 | Visit 7 (Week 12) |
| N01254 | Visit 8 (Week 16) |

The following assessments were to be performed for all subjects at the above time points: laboratory parameters, vital signs, and ECGs; the results for these assessments will be summarized at EV. Other assessments were to be performed at the above time points but will not be summarized. QOLIE-31-P, HADS, EQ-5D and social-professional data were only assessed at the above time points for studies N01252, N01253, and N01254.

The body weight recorded at the above study visits for the previous studies will be summarized for EV.

Subjects in Category 3

Some subjects in category 3 have data available from an SEV at the time of entry into N01199. Laboratory parameters, vital signs, and ECGs collected at SEV will be summarized at EV. If one or more of these assessments were not performed at SEV, or if a subject in category 3 does not have an SEV, then the subject will be excluded from EV for the assessments that were not performed, regardless of the duration of time the subject was not receiving the study drug after the previous study.

QOLIE-31-P, HADS, EQ-5D, and socio-professional data will not be summarized at EV for subjects in category 3 regardless of the duration of time the subject was not receiving study drug after the previous study.

3.2.4 Study periods

The study is divided into 3 periods: Evaluation Period, Down-Titration Period, and Post-Treatment Period. A subject is classified as “discontinued” if the subject has a termination case report form (CRF) or has an early discontinuation visit (EDV). A subject is classified as “completed” if this subject completes the full extent of the study as defined in the protocol at database lock.

A “discontinued” subject can be potentially slotted into the 3 periods of the study. The following algorithms will be used to slot the subject appropriately into the Evaluation Period, Down-Titration Period, and Post-Treatment Period.

- For Evaluation Period, the start date is the date of first dose of BRV, and the following algorithm is used to determine the end date:
 - If the subject enters the Down-Titration Period, then the date of EDV is the end date;
 - If the subject does not enter the Down-Titration Period but meets 1 of the following criteria, the Evaluation Period ends on date of last dose of BRV:
 - Without an EDV but having a termination CRF,
 - With an EDV and having a termination CRF,
 - With an EDV and the date of EDV prior to the database lock date and having no termination CRF.
- A subject is considered entering Down-Titration Period only if the subject has an EDV and at least 1 dose of study drug after the date of EDV, the start date of Down-Titration Period is set as 1 day after the date of EDV, and the Down-Titration Period ends on date of last dose of BRV. A subject without an EDV but having a termination CRF or with an EDV but without any dosing of study drug after the EDV will not have the Down-Titration Period, and no artificial Down-Titration Period will be created for analysis.
- A subject is considered entering the Post-Treatment Period if the subject has at least 1 contact (scheduled visit, unscheduled visit, or telephone contact) after the date of last dose of BRV. The Post-Treatment Period starts 1 day after date of last dose of BRV irrespective of entering the Down-Titration Period, and there is no end date.

A “completed” subject can potentially have Evaluation Period, Down-Titration Period, or Post-Treatment Period. At the time of study termination by the Sponsor, subjects will discontinue the study drug following the down titration process or will be converted without titration to commercial BRV where available; alternatively, subjects may be initiated without down-titration in a managed access program, named patient program, compassionate use program, or similar type of access program as allowed per country specific requirements in addition to legal and regulatory guidelines.

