Titration Period during which the dose of BRV is decreased in steps of 50mg/day on a weekly basis with a last down titration step at 20mg/day for 1 week. Subjects who have completed the Down-Titration Period or subjects who discontinue during the Evaluation Period without entering the Down-Titration Period enter a Post-Treatment Period for a minimum of 2 weeks and a maximum of 4 weeks and subsequently, the final visit will occur.

The maximum allowable daily dose for this study was increased from 150mg/day to 200mg/day based on amendment 6 to the protocol. It is recommended that the daily dose be administered in 2 equal intakes.

Dose adjustment to concomitant AEDs may be made at any time during the study and subjects may start new AEDs. Concomitant AEDs may also be discontinued; however, special considerations apply if the discontinuation of such AEDs results in the subject receiving BRV monotherapy. Previously, in the event of excellent efficacy and tolerability of BRV, withdrawal of concomitant AEDs resulting in monotherapy of BRV may have been attempted by the Investigator. With protocol amendment 6, conversion to monotherapy was no longer permitted; however, subjects already on BRV monotherapy are allowed to continue monotherapy treatment.

The visit schedule for this study depends on the previous study from which the subject was enrolled and the numbering of study visits differs depending on the previous study. Study visits at Months 6, 12, 18, 24, and so forth are either Full Evaluation Visits (FEVs) or Yearly Evaluation Visits (YEVs) at which a greater number of assessments are performed for all subjects from previous studies. For subjects coming from N01193, study visits at Months 1, 3, 5, 15, and 21 are minimal Evaluation Visits (MEVs) at which few assessments are generally performed. Study visits at Months 2, 4, and 9 are FEVs. For subjects coming from N01252, N01253, and N01254, study visits at Months 1, 3, 9, 15, 21 are MEVs. The study visit at Month 2 is an FEV. In addition, a phone call is scheduled at the end of the Down-Titration period and a Drug-Free Final Visit (FV) is scheduled at the end of the Post-Treatment Period. The study schedule just described is shown in [Table 2-1](#).

Table 2–1: Study Schedule

| Subjects coming from Exploratory Study (N01193) | | | Subjects coming from Confirmatory Studies (N01252, N01253, N01254) | | |
|--|-------|---------------|--|-------|---------------|

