Kaplan-Meier estimates of the percentage of subjects completing 3, 6, 12, 24, 36, 48, and 60 months of treatment with BRV will be provided. This analysis will be based on the duration of exposure to BRV as defined in Section 3.2.7. Subjects who have permanently discontinued will be analyzed as events on the last day of treatment with study drug; subjects who complete the study will be censored on the last day of treatment with study drug.

The date of first subject in (date of earliest Visit 1), date of last subject out (date of last scheduled or unscheduled visit), number of enrolled subjects, and the number of subjects in each analysis set or seizure type will be summarized overall and by investigator site.

Subjects who transferred sites will be summarized according to their original site.

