11.1 Extent of exposure

A daily dose will be calculated for each study day from the day of first dose of BRV to the day of last dose of BRV for the purposes of calculating modal dose. Daily dose will be calculated as the sum of the AM and PM dose for each day.

Modal daily doses will be calculated across all study days on or after the day of first dose of BRV and up to and including the day of last dose of BRV. Modal daily dose is the most frequently taken daily dose during this period. In the event of a tie, the modal dose will be set to the lower of the tied doses. Modal daily dose will be categorized as follows:

| Category | Definition |
|-----------|--------------------------|
| 5 mg/day | <20mg/day |
| 20mg/day | ≥20mg/day to <50mg/day |
| 50mg/day | ≥50mg/day to <100mg/day |
| 100mg/day | ≥100mg/day to <150mg/day |
| 150mg/day | ≥150mg/day to <200mg/day |
| 200mg/day | ≥200mg/day |

Subject years of exposure will be calculated by summing the exposure duration in days for all subjects being summarized, and dividing the resulting value by 365.25.

Subject years of exposure will be presented overall and by modal dose for the Safety Analysis Set. The subject years of exposure presented by modal dose will be the total subject years of exposure of subjects with that modal dose.

The number and percentage of subjects exposed to BRV will be summarized overall and by modal dose category. The number and percentage of subjects in each Exposure Duration Cohort (≥3 months, ≥6 months, ≥12 months, and so forth) will be summarized.

The number and percentage of subjects within each modal dose category will be summarized for each Exposure Duration Cohort; percentages will be relative to the total number of subjects in each Exposure Duration Cohort.

In addition to the overall summaries of the above, the above will also be summarized by subgroup for region, and seizure type (Partial Onset Seizures, All Other Seizure Types).

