11.2.2 General summaries of TEAEs

Pre-treatment AEs will be provided in a subject data listing; no summaries of pre-treatment AEs are planned.

An overall summary of AEs will provide the overall number of TEAEs and the numbers and percentages of subjects with at least 1 TEAE, with a TEAE that led to permanent discontinuation of study drug, with a drug-related TEAE, with a severe TEAE, with a treatment-emergent SAE, and with a drug-related treatment-emergent SAE. The number and percentage of subjects who died will also be summarized. This summary will be provided for all subjects in the Safety Analysis Set and also by subgroup for geographic region and seizure type.

The following summaries of TEAEs will be provided by MedDRA SOC and PT. All summaries are for the combined Evaluation, Down-Titration, and Post-Treatment Periods unless otherwise indicated.

Overall Incidence Summaries

- Incidence of TEAEs
- Incidence of TEAEs by 3-month time interval
- Incidence of TEAEs by study period (Evaluation, Down-Titration, Post-Treatment)
- Incidence of TEAEs for TEAEs occurring in at least 5% of subjects
- Incidence of TEAEs by 3-month time intervals for TEAEs occurring in at least 5% of subjects overall
- Incidence of non-serious TEAEs occurring in at least 5% of subjects

The incidence of TEAEs occurring in at least 5% of subjects will be summarized overall as noted above and also by subgroup for geographic region, seizure type, and randomized treatment from the previous double-blind study.

A subject is included in a 3-month interval if the subject was receiving BRV at any time during that interval based on their duration of exposure to BRV (eg, a subject with exposure for 91 days is included in the time interval for Months 1-3 and Months 4-6). Summaries of AEs by 3-month intervals will include all subjects who are classified into each time interval

as defined above. TEAEs which had onset prior to or on the date of the last dose of BRV are included in summaries by 3-month time intervals.

Maximum Intensity and Causality

- Incidence of TEAEs by maximum intensity
- Incidence of drug-related TEAEs

Serious Adverse Events

- Incidence of treatment-emergent SAEs

Discontinuations due to TEAE

- Incidence of TEAEs leading to permanent discontinuation of study drug

TEAEs of interest

AEs of interest will be identified based on MedDRA search criteria, which are documented outside of the SAP. The following summaries will be provided for AEs of interest:

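### TEAE incidence by study period sets crude percentages over years beside percentages over weeks, so a moderate rise in AE rate on stopping BRV would be masked

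*SAP*

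**What the plan says.** - **Periods.** SAP 3.2.4: "The study is divided into 3 periods: Evaluation Period, Down-Titration Period, and Post-Treatment Period". For a discontinued subject, Evaluation starts at the first dose and ends at the EDV, or at the last dose if there is no taper. Down-Titration runs from the day after the EDV to the last dose. Post-Treatment starts the day after the last dose, requires at least one later contact, and applies "irrespective of entering the Down-Titration Period, and there is no end date". For completed subjects, 3.2.4 says that any of the periods may occur but gives no rule for their dates.
- **Planned length after stopping.** SAP 2.3 has subjects "enter a Post-Treatment Period for a minimum of 2 weeks and a maximum of 4 weeks", after which the Final Visit takes place. Protocol 9.3 agrees.
- **Length of Evaluation.** It is not fixed. SAP 5.1 gives a sense of scale: "Kaplan-Meier estimates of the percentage of subjects completing 3, 6, 12, 24, 36, 48, and 60 months of treatment with BRV will be provided".
- **The table.** SAP 11.2.2 lists, by SOC and PT, "Incidence of TEAEs by study period (Evaluation, Down-Titration, Post-Treatment".
- **The statistic.** SAP 3.1: "All summaries will be descriptive; no statistical hypothesis testing is planned". Categorical variables get counts and percentages. The general rule is "Denominators for percentages will generally be based on the set of subjects with at least 1 assessment at the time point", or with an assessment in the interval summarized. Nothing more specific is written for the by-period AE table.
- **Time at risk.** SAP 11.1: "Subject years of exposure will be presented overall and by modal dose for the Safety Analysis Set". The same section repeats this by region and seizure type. Subject-years are not planned by study period, nor as a denominator for AEs.

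**The concern.** The percentage of subjects with at least one event grows with the time observed, even when the event rate is constant. Columns covering years and columns covering weeks are therefore not on one scale.

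This matters because the by-period table is the only planned TEAE summary that isolates time during and after withdrawal. The other TEAE summaries in SAP 11.2.2 pool all three periods unless stated otherwise. The 3-month interval tables count from the first dose and keep only events with onset up to the last dose, so they merge taper time with Evaluation time and omit Post-Treatment.

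Long-term safety and tolerability is the primary objective, and occurrence of a TEAE is a primary safety variable. A reader scanning across the three columns could see lower percentages in the two short periods when the underlying rate had in fact risen several-fold.

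**Working it through.** There is no plan figure to reproduce: the documents give no AE rate, no sample size calculation and no tests. The check is illustrative, and its assumptions are marked.

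**Inputs**
- Down-Titration: protocol 9.3 allows weekly steps of at most 50 mg/day and ends with one week at 20 mg/day. At the largest steps this takes 1, 2, 3 and 4 weeks from 50, 100, 150 and 200 mg/day. These are minimum lengths.
- Post-Treatment: 14 to 28 days as planned (SAP 2.3).
- Evaluation: 180 to 1800 days (assumed single lengths; 1800 days is the 60-month point on the SAP's 30-day month).
- Event rate: r = 0.10 per subject-year in Evaluation (assumed), multiplied by k on stopping.

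**Formula.** Percentage with an event = 1 − exp(−r × days / 365.25).

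**Short periods at r = 0.10**

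| Length | k = 1 | k = 2 | k = 3 | k = 5 | k = 10 |
|---|---|---|---|---|---|
| 1 week | 0.19% | 0.38% | 0.57% | 0.95% | 1.90% |
| 4 weeks | 0.76% | 1.52% | 2.27% | 3.76% | 7.38% |

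**Evaluation, and the rise needed just to match it.** Setting the two percentages equal gives k = Evaluation days / period days, whatever the value of r.

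| Evaluation | % at r = 0.10 | k to match, 4 weeks | k to match, 1 week |
|---|---|---|---|
| 180 days | 4.8% | 180/28 = 6.4 | 180/7 = 25.7 |
| 360 days | 9.4% | 360/28 = 12.9 | 360/7 = 51.4 |
| 720 days | 17.9% | 720/28 = 25.7 | 720/7 = 102.9 |
| 1800 days | 38.9% | 1800/28 = 64.3 | 1800/7 = 257.1 |

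A 10-fold rise over 4 weeks stays below the Evaluation percentage once Evaluation exceeds 10 × 28 = 280 days. With shorter Evaluation the masked range is narrower.

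**Sensitivity to the rate.** At r = 1.0 and 720 days, Evaluation prints 86.1%. Four weeks prints 7.4% with no change in rate and 20.5% at 3-fold. The matching ratio is still 25.7.

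**Against a 90-day interval.** The matching ratio falls to 90/28 = 3.2 for 4 weeks and 90/7 = 12.9 for 1 week.

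**Effect of the open end.** At a constant r = 0.10, the Post-Treatment column reads 0.38% at 14 days, 0.76% at 28 days, 2.4% at 90 days and 9.5% at 365 days.

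**Effect of the denominator.** Suppose 200 subjects (assumed) taper for 4 weeks at k = 5. Then 3.76% × 200 = 7.5 subjects have an event. Over all 668 enrolled, that would print as 7.5/668 = 1.1%.

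**The case against.** The strongest reply is that the SAP delivers what protocol 13.1.3 asks for, incidence tables by period. Everything is descriptive, withdrawal effects are not a stated objective, and nothing in the SAP tells a reader to rank the columns. All of that is true. It bears on priority, but it does not make the percentages comparable.

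Two stronger readings are tempting and are not supported.

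- **A reader might infer that a withdrawal signal cannot show at all.** The table has separate Down-Titration and Post-Treatment columns by SOC and PT, so an event type that appears only on stopping would be seen, as would a very large rise. Data listings are planned, and SAP 3.2.2 gives days after the last dose their own numbering, so onset after stopping can be traced.
- **A reader might infer that Post-Treatment follow-up is unbounded in practice.** The missing end date is a feature of the SAP definition. For subjects who stop the drug, the Final Visit is scheduled after 2 to 4 drug-free weeks, and protocol 12.2.2 asks for SAEs known up to 30 days after withdrawal. An open end would also raise the Post-Treatment percentage, the opposite of masking. Its real harm is that subject-time cannot be computed.

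The 3-month interval table does offer a fixed-length reference on treatment, against which a smaller rise would show. It stands as a partial aid only, because it mixes in taper time and stops at the last dose.

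Tapers slower than the largest steps are permitted, which would lengthen Down-Titration and lower the matching ratio. Rates in the short periods will be imprecise. Both points favour reporting subject-time.

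**Conclusion.** The point holds in a limited form, as a cheap improvement. The by-period table compares crude percentages over very unequal times, and no planned output supplies the period durations or subject-time needed to turn them into rates. A moderate rise on withdrawal, roughly 2- to 10-fold, would print below the Evaluation percentage. How far this extends depends on the length of Evaluation: for a 4-week period the break-even rise is 6.4-fold at 180 days and 25.7-fold at 720 days.

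The break-even ratios assume a constant rate within each period and one representative Evaluation length, but not any particular AE rate. The printed percentages depend on the assumed rate as well. The documents supply neither the rates nor the achieved Evaluation lengths.

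One further gap affects interpretation. SAP 3.2.4 allows subjects at study termination to move without taper to commercial BRV or an access program. Such a subject with a later contact could be placed in Post-Treatment while still taking BRV.

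**What to change.** **SAP 11.2.2, by-period table**
- State the denominator for each column as the subjects who enter that period.
- Add, for each period, total subject-time and TEAE onsets per subject-year. Give these overall and by SOC, and by PT only for common events.
- Keep the crude percentages alongside.

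**SAP 3.2.4**
- Close Post-Treatment subject-time at the Final Visit or, if there is none, at the last contact.
- State the period start and end dates for completed subjects.
- Exclude from Post-Treatment, or show separately, subjects who moved directly to commercial BRV or another BRV supply.

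**Cost.** No new data collection is needed. There is some programming: period dates for completed subjects, an end rule, and event counts with subject-time in three columns. Short-period rates will be imprecise. If 200 subjects (assumed) taper for 4 weeks, subject-time is 200 × 28/365.25 = 15.3 years, so at 0.10 per subject-year about 1.5 events are expected, or 7.7 at a 5-fold rise. With a 1-week taper it is 3.8 years, and about 0.4 or 1.9 events. For comparison, 668 subjects over an assumed 720 days give about 1317 subject-years and 132 events in Evaluation. Showing the subject-time beside each rate makes that imprecision plain, and it is the reason to limit PT-level rates to common events.
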